#### 10.1.3 Unexpected Adverse Reaction

An unexpected adverse reaction is an adverse reaction, the nature and severity of which is not consistent with the applicable product information (e.g., Investigator's Brochure for an unapproved investigational product or package insert/summary of product characteristics for an approved product).

# **10.1.4** Laboratory Test Abnormalities

The Qualified Investigator must assess the clinical significance of all abnormal laboratory values as defined by the compendium of normal values for the reference laboratory.

Any study emergent abnormal laboratory result which is clinically significant, i.e., meeting one or more of the following conditions, should be recorded as a single diagnosis on the AEs form in the study record:

- 1. Accompanied by clinical symptoms
- 2. Leading to interruption or discontinuation of the investigational product
- 3. Requiring a change in concomitant therapy

This applies to any protocol and non-protocol specified laboratory result from tests performed after the first dose of the investigational product, which falls outside the laboratory reference range and meets the clinical significance criteria for liver and kidney tests as well as for hematology and clinical chemistry, etc. (i.e. AST and/or  $ALT > 2 \times ULN$ ).

This does not apply to any abnormal laboratory result which falls outside the laboratory reference range but which does not meet the clinical significance criteria or those which are a result of an AE which has already been reported.

Any laboratory result abnormality fulfilling the criteria for an SAE should be reported as such, in addition to being reported as an AE in the study record.

two products on supporting immune function in healthy adults

### 10.2 Treatment and Follow-Up of AEs And Laboratory Abnormalities

## **10.2.1** Treatment and Follow-up of AEs

Adverse Events, especially those for which the relationship to the investigational product is suspected, should be followed up until they have returned to baseline status or stabilized.

If after follow-up, return to baseline status or stabilization cannot be established, an explanation should be recorded in the study record.

### 10.2.2 Treatment and Follow-up of Laboratory Abnormalities

In the event of participant-initiated withdrawal or clinically significant unexplained abnormal laboratory test values, the participant will be withdrawn from the investigational product or placebo and will remain in the study and be required to attend all remaining study visits as part of a safety arm.

#### 10.3 Reporting of SAEs And Unexpected Adverse Reactions

The Qualified Investigator will be responsible for classification of an AE as an SAE within 24 hours of notification. Causality should be signed off by the Qualified Investigator prior to reporting to ethics and regulatory bodies. Notification of any serious adverse events must be made in writing to the study Sponsor. The IRB will be notified of all product related SAEs and unexpected adverse reactions. All blinded SAE's or unblinded-participant-on-active product SAE's will be reported to the Therapeutics Products Directorate (TPD) in an expedited manner.

KGK Science Inc. must notify the TPD of all blinded or unblinded-participant-on-active product serious adverse events and reactions as follows:

If it is neither fatal or life threatening, within 15 calendar days after the day on which the Sponsor becomes aware of the information; and

If it is fatal or life threatening, must be reported as soon as possible, but not later than seven (7) days after the day on which the Sponsor becomes aware of the information.

#### 11 STATISTICAL EVALUTION

#### 11.1 Determination of Sample Size

The planned total sample size will be 75 with 25 participants randomized to each study group. This sample size will enable detection of a difference in CD3+ of 10.8%, difference in CD4+ of 6.5%, difference in CD8+ of 4.9%, difference in CD45+ of 16.7% and difference in NK cells (CD56+) of 4.4% for lymphocytes; difference in IgA of 67 mg/dL (0.67 g/L), difference in IgG of 440 mg/dL (4.4 g/L), and difference in IgM of 133 mg/dL (1.33 g/L) for and immunoglobulins among the three arms at an overall 5% significance level and 80% power. This sample size takes into account a loss to follow up rate of 20%. The calculation is based on the studies by Olivares et al (19, 36, 37).

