#### **Primary outcome:**

The difference between UP360, UP446 and placebo in the increase in immune parameters as assessed by lymphocyte populations (CD3+, CD4+, CD8+, CD45+, TCRγδ+, CD3-CD16+56+) and immunoglobulins (IgG, IgM, and IgA) in blood from baseline at Day 28 and 56

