# 11.3 Statistical Analysis Plan

All the primary and secondary endpoints will be analyzed as continuous variables.

For each primary and secondary endpoint, descriptive statistics including number of subjects, arithmetic mean, standard deviation, median, minimum and maximum values will be presented for each study day and for the changes from baseline (Day 0) to each subsequent study day.

Changes in continuous endpoints from baseline will be calculated as:

Change to 
$$V_i = Value$$
 at  $V_i - Value$  at  $V_{baseline}$ 

Differences in changes between groups will be assessed by repeated measures mixed model ANOVA, with study group and visit as the fixed effects. Each model will include the baseline value as a covariate. Within group changes will be assessed by the paired t-test or Wilcoxon Sign Rank test, depending on the distribution of the data. All tests of significance for primary outcomes will be performed at one-sided, and for secondary outcomes will be performed at two-sided, alpha level = 0.05 unless otherwise specified.

The co-primary outcomes will be interpreted individually and together as a real-life global assessment of immune function. As such, there will be no adjustment for multiple outcomes (38-42). This is in accordance with the following principles of the American Statistical Association's statement on statistical significance

and p-values: #3 – "scientific conclusions and business or policy decisions should not be based only on whether a p-value passes a specific threshold;" #4 – "proper inference requires full reporting and transparency;" and #6 – "by itself, a p-value does not provide a good measure of evidence regarding a model or hypothesis" (43).

Missing data for the primary and secondary endpoints will be imputed with last-observation-carried-forward (LOCF) method or multiple imputation as a sensitivity analysis for ITT Population. No imputation will be performed for PP and Safety Population.

Probabilities  $\leq 0.05$  will be considered statistically significant. All statistical analysis will be completed using the R Statistical Software Package Version 3.6.3 or newer for Microsoft Windows (44).

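### Section 11.1 claims an overall 5% significance level that the unadjusted one-sided 5% tests in Section 11.3 do not provide

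*Protocol*

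**What the plan says.** Section 11.1 lists detectable differences for eight markers, with 25 participants per arm and 20% loss to follow-up, "among the three arms at an overall 5% significance level and 80% power".

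Section 5 defines the primary outcome as "lymphocyte populations (CD3+, CD4+, CD8+, CD45+, TCRγδ+, CD3-CD16+56"+), that is six lymphocyte populations, "and immunoglobulins (IgG, IgM, and IgA) in blood from baseline at Day 28 and 56". That makes nine markers at two visits, compared between UP360, UP446 and placebo.

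Section 11.3 sets the testing rules:
- On sidedness: "All tests of significance for primary outcomes will be performed at one-sided", with alpha 0.05.
- On the threshold: probabilities of 0.05 or less "will be considered statistically significant".
- On interpretation: "The co-primary outcomes will be interpreted individually and together as a real-life global assessment of immune function".
- On multiplicity: "there will be no adjustment for multiple outcomes".

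The protocol states no testing order, gatekeeping test, global test or rule that all outcomes must succeed.

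**The concern.** An overall level is the probability of any false-positive result in the family of tests that it covers. Section 11.1 attaches one such level to a joint list of markers and three arms. Section 11.3 gives every primary test its own 5% and lets any of them be read alone. Both statements cannot be true of the same design.

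The primary result is the efficacy evidence for two products. If the sample-size section is quoted in a report or publication, a significant finding on one marker would appear to carry a 5% trial-wide false-positive risk when the actual risk is larger. The multiplicity argument in Section 11.3 speaks of multiple outcomes; it does not mention the two products or the two visits.

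**Working it through.** **Inputs.** From Section 11.1: 25 per arm, 20% loss, 80% power, overall 5%. From Section 11.3: one-sided alpha 0.05 per primary test, no adjustment. From Section 5: 6 + 3 = 9 markers, 2 visits, 3 arms. Assumed, because the protocol gives none: correlations between markers and between visits, varied from 0 to 0.9.

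**The plan's own figures.** The loss allowance reproduces: 20 / (1 − 0.20) = 25 per arm. The detectable differences cannot be reproduced, because no standard deviations are given. The overall 5% does not reproduce under any count of tests below.

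**Number of tests.** This is derived, not stated.
- Each marker, visit and product against placebo: 9 × 2 × 2 = 36.
- Visits pooled: 9 × 2 = 18.
- One three-arm test per marker: 9.

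**Smallest case: one marker, one visit, two products against placebo.** The shared placebo arm gives the two test statistics a correlation of 0.5. With z = 1.645, the chance that at least one exceeds it is 1 − Φ₂(1.645, 1.645; 0.5) = 0.0878, about 9%.

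**Ceiling with uncorrelated markers and visits, shared placebo.**
- 36 tests: 1 − (1 − 0.0878)^18 = 0.81.
- 18 tests: 1 − (1 − 0.0878)^9 = 0.56.
- 9 three-arm tests: 1 − 0.95^9 = 0.37.

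**With correlation** (simulation of normal test statistics under no effect, shared placebo, exchangeable marker correlation):

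| Marker / visit correlation (assumed) | 36 tests | 18 tests | 9 tests |
|---|---|---|---|
| 0 / 0 | 81% | 56% | 37% |
| 0.3 / 0.5 | 63% | 44% | 33% |
| 0.7 / 0.7 | 40% | 28% | 21% |
| 0.9 / 0.9 | 24% | 19% | 13% |

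The visit correlation matters only for the 36-test column. The expected number of false-positive tests does not depend on correlation: 36 × 0.05 = 1.8, 18 × 0.05 = 0.9, 9 × 0.05 = 0.45.

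**Cost of a true overall 5%** (two-sample t-test, 20 evaluable per arm, 80% power): the detectable difference is 0.80 SD at one-sided 5% and 0.91 SD at one-sided 2.5%, the first Holm step across two products.

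**The case against.** The strongest reply is that the sponsor hides nothing. Section 11.3 declares the absence of adjustment, argues for it and cites support. A reader might infer from the figures above that non-adjustment is itself the error, or that it was concealed. The protocol supports neither inference. Not adjusting is an argued policy, and the defect is only that Section 11.1 claims an overall level alongside it.

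A second reply is that *overall* may mean only across the three arms for each marker, since Section 11.1 lists differences marker by marker. This has some force. One omnibus three-arm test of a single marker would hold 5% for that marker. But Section 11.3 names no such gate, one-sided tests fit poorly with an omnibus test, and without a gate two contrasts already give about 9%.

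A third reply concerns the count. Section 11.3 describes a repeated-measures model with group and visit effects and mentions no interaction, which could mean one group effect per marker, pooled over visits. So 36 is a reasonable reading but not a documented one, and the lower counts belong beside it. Contrasts and visit handling may also be left to a statistical analysis plan that is not shown; their absence from the protocol is not the point here.

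Two larger statements are tempting. One is 84%, from 1 − 0.95^36. It requires 36 independent tests, which is impossible when both products share a placebo arm. The other is that a false-positive primary result is more likely than not. That holds in some of the assumed settings and fails in others, and the protocol gives no correlations from which to choose.

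**Conclusion.** The inconsistency between Sections 11.1 and 11.3 stands. None of the counts examined here, from the smallest to the largest, gives an overall 5% level under the rules as written.

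The size is uncertain. It depends on a test count that the protocol does not state and on correlations that had to be assumed. The direction does not depend on them: across the nine markers, even the most lenient count at the highest assumed correlation leaves the risk at more than twice the claimed level. The 24% at correlations of 0.9 is the low end of the assumed range, not a proven floor.

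**What to change.** **Needed.** In Section 11.1, replace the overall 5% claim with: *one-sided 5% per comparison, not adjusted for multiple markers, visits or products*. The sponsor should confirm that the listed differences were calculated at that level, since Section 11.1 does not give the sidedness and the missing standard deviations prevent a check. In Section 11.3, add that the trial-wide false-positive rate is therefore above 5%, and that an isolated p ≤ 0.05 on one marker will not be presented as trial-level confirmation. This costs two sentences, changes neither the sample size nor the analysis, and keeps the sponsor's policy of no adjustment.

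**Optional, only if a true overall 5% is wanted.** Pre-specify one primary test per product, for example a global score in line with the plan's idea of a global assessment, and apply Holm across the two products. The remaining markers and visits would be reported as supportive estimates. This is a redesign, because the protocol ranks neither markers nor visits. It needs no more participants, but the detectable difference rises from about 0.80 to 0.91 SD at 20 evaluable per arm.

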#### 11.2 Analysis Plan

The **Safety Population** will consist of all participants who received any amount of study product or placebo, and on whom any pre- or post-randomization safety information is available.

The **Intent-to-Treat (ITT) Population** consists of all participants who received study product or placebo and on whom any post-randomization effectiveness information is available.

The **Per Protocol** (**PP**) **Population** consists of all participants who consumed at least 80% of study product or placebo doses, do not have any protocol deviations that affect primary outcomes and complete all study visits and procedures connected with measurement of the primary variables.

# 11.3 Statistical Analysis Plan

All the primary and secondary endpoints will be analyzed as continuous variables.

For each primary and secondary endpoint, descriptive statistics including number of subjects, arithmetic mean, standard deviation, median, minimum and maximum values will be presented for each study day and for the changes from baseline (Day 0) to each subsequent study day.

Changes in continuous endpoints from baseline will be calculated as:

Change to 
$$V_i = Value$$
 at  $V_i - Value$  at  $V_{baseline}$ 

Differences in changes between groups will be assessed by repeated measures mixed model ANOVA, with study group and visit as the fixed effects. Each model will include the baseline value as a covariate. Within group changes will be assessed by the paired t-test or Wilcoxon Sign Rank test, depending on the distribution of the data. All tests of significance for primary outcomes will be performed at one-sided, and for secondary outcomes will be performed at two-sided, alpha level = 0.05 unless otherwise specified.

The co-primary outcomes will be interpreted individually and together as a real-life global assessment of immune function. As such, there will be no adjustment for multiple outcomes (38-42). This is in accordance with the following principles of the American Statistical Association's statement on statistical significance

and p-values: #3 – "scientific conclusions and business or policy decisions should not be based only on whether a p-value passes a specific threshold;" #4 – "proper inference requires full reporting and transparency;" and #6 – "by itself, a p-value does not provide a good measure of evidence regarding a model or hypothesis" (43).

Missing data for the primary and secondary endpoints will be imputed with last-observation-carried-forward (LOCF) method or multiple imputation as a sensitivity analysis for ITT Population. No imputation will be performed for PP and Safety Population.

Probabilities  $\leq 0.05$  will be considered statistically significant. All statistical analysis will be completed using the R Statistical Software Package Version 3.6.3 or newer for Microsoft Windows (44).

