#### **Secondary outcomes:**

The difference between UP360, UP446 and placebo at Day 28 and 56 in:

- 1. Number of confirmed COVID-19 infections
- 2. Number of confirmed flu cases
- 3. Impact of COVID-19 on quality of life assessed by the COVID-19 Impact on QoL Questionnaire
- 4. Over-the-counter cold and flu medication use

The difference between UP360, UP446 and placebo at Day 56 in:

- 1. Number of hospitalizations due to COVID-19
- 2. Number of hospitalizations due to flu

The difference in change between UP360, UP446 and placebo from baseline at Day 28 and 56 in:

- 1. Erythrocyte sedimentation rate (ESR) and C-reactive protein (CRP)
- 2. Hematology parameters: white blood cell (WBC) count with differential (neutrophils, lymphocytes, monocytes, eosinophils, basophils), reticulocyte count, red blood cell (RBC) count, hemoglobin, hematocrit, platelet count, RBC indices (mean corpuscular volume (MCV), mean corpuscular hemoglobin (MCH), mean corpuscular hemoglobin concentration (MCHC), and red cell distribution width (RDW)
- 3. Complement C3 and C4 proteins
- 4. Mean global severity index, as measured by area under the curve (AUC) for the Modified Wisconsin Upper Respiratory Symptom Survey (WURSS)-24 daily symptom scores
- 5. Mean symptom severity scores, as measured by AUC for the WURSS-24 daily severity symptom scores
- 6. Number of well days (defined as days scored as 0 (not sick) for the question, "How sick do you feel today?") as assessed by the Modified WURSS-24 Questionnaire
- 7. Number of sick days (defined as days scored as any number from 1 through 7 (sick) for the question, "How sick do you feel today?") as assessed by the Modified WURSS-24 Questionnaire
- 8. Frequency of common upper respiratory tract infection (UTRI) symptoms as assessed by the Modified WURSS-24 Questionnaire
- 9. Duration of common UTRI symptoms as assessed by the Modified WURSS-24 Questionnaire
- 10. Severity of common UTRI symptoms as assessed by the Modified WURSS-24 Questionnaire
- 11. Vitality and quality of life as assessed by the Vitality and Quality of Life (QoL) Questionnaire

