# 7.2 Exclusion Criteria

- 1. Women who are pregnant, breast feeding, or planning to become pregnant during the study
- 2. Participant has a known allergy to the active or inactive ingredients in UP360, UP446, placebo, or QIV
- 3. Unvaccinated participants with flu prior to baseline from September 2020 or prior to Day 28 vaccination
- 4. Participants self-reporting a diagnosis of COVID-19 prior to baseline or prior to Day 28 vaccination
- 5. Participants who have received the COVID-19 vaccine
- 6. Current use of prescribed immunomodulators (including corticosteroids) such as immunosuppressants or immunostimulants within 4 weeks of baseline (see Section 7.3)
- 7. Current use of dietary supplement or herbal medicines associated with boosting or modulating the immune system unless willing to washout (see Section 7.3.2)

- 8. Participation in other clinical research studies 30 days prior to enrollment will be assessed on a caseby-case basis by the QI
- 9. Individuals who are unable to give informed consent
- 10. Any other condition, chronic disease, or lifestyle factor, that, in the opinion of the QI, may adversely affect the participant's ability to complete the study or its measures or pose significant risk to the participant

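### The rule that every secondary endpoint is analysed as a baseline-adjusted continuous variable does not fit the four infection and hospitalisation outcomes

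*Protocol*

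**What the plan says.** Section 11.3 opens with a rule that has no exception: "All the primary and secondary endpoints will be analyzed as continuous variables". It then asks for means, standard deviations and changes from baseline for each primary and secondary endpoint. The one between-group method is this: "Differences in changes between groups will be assessed by repeated measures mixed model ANOVA, with study group and visit as the fixed effects". The next sentence adds: "Each model will include the baseline value as a covariate". Testing is "for secondary outcomes will be performed at two-sided, alpha level = 0.05 unless otherwise specified". The protocol names no method for binary or count data.

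The secondary outcomes in section 5 include "Number of confirmed COVID-19 infections" and "Number of confirmed flu cases", compared at Day 28 and Day 56. They also include "Number of hospitalizations due to COVID-19" and the matching outcome for flu, both compared at Day 56 only. Over-the-counter cold and flu medication use is listed with the infections.

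The exclusion criteria in section 7.2 include "Participants self-reporting a diagnosis of COVID-19 prior to baseline or prior to Day 28 vaccination". A parallel criterion covers unvaccinated people with flu since September 2020. Section 9.5 removes COVID-19 and flu cases that arise before the Day 28 vaccination. Section 9.7 removes COVID-19 cases that arise after it.

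**The concern.** A model for a continuous response with baseline adjustment needs a response that varies on a scale and a baseline that differs between participants. The four event outcomes offer neither. Within eight weeks a participant has or has not had COVID-19, flu, or an admission for one of them, and by eligibility no one starts with an event.

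The summaries prescribed for these outcomes (mean, standard deviation, change from baseline) are therefore uninformative, and the prescribed model has terms that cannot be estimated. Whoever runs the analysis must improvise by dropping terms, switching method or reporting nothing, and would do so after seeing how many events occurred. Section 11.3 treats p ≤ 0.05 as significant, so the choice of method can decide whether a difference in infections is declared. Section 4 says the findings may inform public health policy on influenza and COVID-19, so these results should rest on a method fixed in advance.

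**Working it through.** **Inputs.** 75 participants, 25 per arm (section 11.1); two-sided 0.05 for secondary outcomes (11.3); baseline event status 0 for all eligible participants (7.2). The protocol gives no event rates, so every rate below is an assumption. It also states no figure for these outcomes, so there is nothing to reproduce.

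**Step 1: can the model be fitted as written?**
- *Infections (Day 28 and Day 56).* The columns are intercept, two arm terms, visit and baseline: 5 columns. Baseline is all zeros, so the rank is 4. Adding the two arm-by-visit terms gives 7 columns and rank 6. The baseline coefficient cannot be estimated in either form.
- *Hospitalisations (Day 56 only).* With one visit the visit column is constant and the arm-by-visit columns repeat existing ones. The rank is 3 (intercept and two arms) out of 5, or out of 7 with the interaction. No repeated measure is left.
- *No events of a type.* Between-arm and within-arm sums of squares are both 0, so F = 0/0. The probability of no event is (1 − r)^75, where r is the risk assumed equal in all arms:

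| Assumed risk r | P(no event in 75) |
|---|---|
| 0.5% | 0.69 |
| 1% | 0.47 |
| 2% | 0.22 |
| 5% | 0.02 |

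**Step 2: who is left in the per-visit means?** A case before Day 28 is removed (9.5) and may have no Day 56 value. The same holds for COVID-19 cases after vaccination (9.7). The per-protocol set in 11.2 requires all visits and procedures connected with the primary variables, so cases removed early fall out of it. A mean over participants present at Day 56 can thus omit those who had the event.

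**Step 3: does the test matter when events are few?** This uses a one-way comparison of three arms of 25 on 0/1 data. With 2 and 72 degrees of freedom, the F-test p-value equals (SSW/SST)^36. For a 3-0-0 split:
- SSW = 3 × (1 − 3/25) = 2.64
- SST = 3 − 3²/75 = 2.88
- F-test p = (2.64/2.88)^36 = 0.044
- Exact (Freeman-Halton) p = 3 × C(25,3)/C(75,3) = 6,900/67,525 = 0.102

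| Split | F-test p | Exact p |
|---|---|---|
| 2-0-0 | 0.132 | 0.324 |
| 3-0-0 | 0.044 | 0.102 |
| 4-0-0 | 0.0135 | 0.031 |
| 4-1-0 | 0.062 | 0.119 |

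Of these splits only 3-0-0 changes sides of 0.05. Given exactly three events in total, the F-test rejects with probability 0.102 under no difference.

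**Step 4: is type I error inflated overall?** All outcomes were enumerated under equal risk in the arms. The three-arm F-test rejects 0.06% of the time at r = 0.5%, 0.35% at 1%, 1.5% at 2%, 3.5% at 5% and 4.2% at 15%. Its maximum is 5.2%, at r = 50%. The pairwise t-test at 25 against 25 rejects 0.02% at r = 1%, 2.0% at 5% and 5.5% at 15%. Averaged over event counts, the normal-theory test is conservative where events are rare.

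**The case against.** Several counter-arguments have force.

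- *The reach of the ANOVA is inferred.* The ANOVA sentence concerns differences in changes, while section 5 lists the event outcomes as differences at a visit. No sentence says outright that events go into this model. That stands. The inference rests on the blanket opening sentence and on the absence of any other method, and the opening sentence is unsuitable for these outcomes on either reading.
- *Rank deficiency is not fatal.* A reader might infer that the analysis cannot be run at all. It can: once the redundant terms are dropped, the arm contrast is estimable unless no event occurs. With no events an exact test is uninformative too.
- *P-values are not too small in general.* A reader might infer inflated type I error, for example from 4 of 25 against 0 of 25, where the t-test gives 0.038 and Fisher's test 0.110. Step 4 does not support that. Much of this gap is Fisher's own conservatism: Barnard's unconditional exact test gives 0.041. What remains is disagreement in particular sparse splits, such as 3-0-0.
- *Over-the-counter use is different.* It need not be yes/no, nobody is excluded for it, and concomitant medication is recorded in the run-in diary (9.1). The constant-baseline argument does not reach it.
- *Loss of cases is possible, not certain.* Section 7.5 asks for end-of-study evaluations at withdrawal where possible, and 11.3 foresees imputation for the intent-to-treat set. This softens Step 2, but neither sets the denominator for an event outcome.

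It might also be said that a separate statistical analysis plan will settle this. But the protocol does not leave the matter open. It states a rule, and a later plan could avoid it only by departing from the protocol.

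**Conclusion.** The point holds in a limited form. Section 11.3 fixes a continuous, baseline-adjusted analysis for four secondary outcomes that are events with a baseline of zero. The model as written is rank-deficient for all four, has no repeated measure for the two hospitalisation outcomes, and has no defined F test if no event occurs. The chance of no event is 22% to 69% at assumed risks of 2% down to 0.5%. With few events the conclusion can depend on the test (0.044 against 0.102 for 3-0-0), but there is no general inflation of type I error and the arm comparison is not lost altogether. The result rests on 25 participants per arm, on baseline event status being zero through the exclusion criteria, and on reading the blanket rule as covering these outcomes. They are secondary outcomes, and the primary immune-marker analysis is not affected. The sponsor should correct this, since the remedy is simple.

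**What to change.** In section 11.3, restrict the continuous-variable rule to continuous endpoints, and add:
- **COVID-19, flu and hospitalisation for each:** number of participants with at least one event out of all randomised, by arm. Give risk differences with exact or score intervals and one exact test named in advance (for example Fisher's or an unconditional exact test), with no baseline covariate. Hospitalisations may be reported descriptively only.
- **Over-the-counter cold and flu medication:** analyse as a proportion of users or as a count. The run-in value may stay as a covariate.

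The denominator of all randomised means that a participant removed after an infection still counts as a case. The cost is wording in 11.3 only, with no extra participants, visits or samples. Some p-values will be less favourable than under the present rule.
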